3.2 Estimation of overall efficacy

Logistic regression will be used to assess the overall efficacy of the intervention, including data from all 142 facilities. We anticipate varying intervention effects per region and per facility level and depending on whether the facility was part of SBBC phase I or not, and possibly also varying intervention effects between combinations of these factors. Further, we anticipate time-varying intervention effects as well as clustering on two levels, birth (for multiples) and facility.

Thus, the full model will be a mixed-effects logistic regression model, incorporating the following:

Fixed effects:

- a) Time-varying intervention effects modelled using a continuous variable representing time since intervention start (set to zero for all baseline observations). To capture potential nonlinear effects, time will be modelled using splines. The spline-transformed time variable, f(t), will be interacted with an indicator for intervention status (intervention vs. baseline), i.e., I(intervention).
- b) Region-specific treatment effects, modeled through an interaction between region (five regions) and the intervention-by-time spline term, $I(\text{intervention}) \cdot f(t)$.
- c) Facility level-specific treatment effects, modeled through an interaction between facility level (three levels) and $I(\text{intervention}) \cdot f(t)$.
- d) Differing treatment effects between facilities that were part of SBBC phase I and those new in SBBC phase II, through interaction between SBBC-I (yes/no) and I(intervention) $\cdot f(t)$.
- e) All higher level interactions between region, facility level, SBBC-I, and $I(\text{intervention}) \cdot f(t)$.

Random effects:

f) Random effects (random intercepts and random intervention effects) for facilities and for births nested within facilities.

In Stata syntax, the full regression model looks like this:

```
i.region i.facility_level i.sbbc_phase1 i.intervention ///
i.intervention#c.s_time ///
i.region#i.intervention#c.s_time ///
i.facility_level#i.intervention#c.s_time ///
i.sbbc_phase1#i.intervention#c.s_time ///
i.region#i.facility_level#i.intervention#c.s_time ///
```

```
i.region#i.sbbc_phase1#i.intervention#c.s_time ///
i.facility_level#i.sbbc_phase1#i.intervention#c.s_time ///
i.region#i.facility_level#i.sbbc_phase1#i.intervention#c.s_time ///
|| facility_id: i.intervention i.intervention#c.s_time ///
|| birth_id: i.intervention i.intervention#c.s_time ///
, covariance(unstructured)
```

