In the (likely) case of convergence problems, the model will be reduced in the following order:

- 1. Reducing complexity in the random effects.
- 2. Reducing complexity in the fixed effects by removing higher order interactions.
- 3. Reducing complexity in the fixed effects by reducing the degrees of freedom for the splines of time, ultimately assuming linear effect of time.
- 4. After each reduction in fixed effects, try in the random effects again.

Regarding 1: Experience from SBBC phase I was that the clustering on birth level (for multiples) was difficult to account for without convergence issues. If the same problem is encountered here and not resolved by removing random intervention effects at two levels, we will resort to the same solution as used in phase I, i.e., including only one of the babies in births with multiples.

Once a model has been identified that converges successfully and shows no signs of numerical instability, we will proceed to reducing the fixed effects structure by optimizing Akaike's Information Criterion (AIC). Specifically, any parameter whose removal results in a reduction of the AIC by at least 2 will be excluded from the model. If possible, random effects will be reintroduced.

In SBBC-I, FHR at admission was by far the most important individual-level adjustment variable for perinatal deaths, and for maternal deaths, FHR at admission and ASB were most important. Referral-in (yes/no) was also of some importance. FHR at admission and referral-in are only available in the intervention period here and only on facility level (FHR also in a less informative variable than in SBBC-I), and this is also the case with preterm (yes/no). Thus, in addition to ASB (for maternal outcome), we will in the current analyses have to suffice with adjusting for birth weight (categorical including "missing" as a category), mother's age (non-linear effect), and multiples (yes/no), which all were found to have some adjustment effect in SBBC-I. Since we do not expect changes in the population during the study period, these adjustments will be mostly relevant for comparisons between regions, facility levels, and SBBC-I (yes/no), where changes in referral patterns among the participating facilities during the intervention may play a role.

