The overall effect of intervention will be presented as the marginal relative risk (RR) at 1.5 years after start intervention, obtained using g-computation (Snowden et al, 2011). Maximum likelihood estimation will be used for model fitting, the final model will be fitted using restricted maximum likelihood.

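### The AIC removal rule in SAP section 3.2 cannot remove any one-degree-of-freedom parameter, so it contradicts its stated aim, and the unit of removal is left open

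*SAP*

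**What the plan says.** Section 3.2 of the SAP sets up a mixed-effects logistic model in which the intervention-by-time spline interacts with region, facility level and SBBC phase I membership, and adds "All higher level interactions between region, facility level, SBBC-I, and" that spline term. Four numbered steps shrink this model if it fails to converge. Once a stable model is found, a separate step follows: "we will proceed to reducing the fixed effects structure by optimizing Akaike's Information Criterion (AIC"). The next sentence makes this specific: "any parameter whose removal results in a reduction of the AIC by at least 2 will be excluded from the model".

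On estimation, the same section states "Maximum likelihood estimation will be used for model fitting", and then "the final model will be fitted using restricted maximum likelihood". The resulting model supplies the marginal relative risk at 1.5 years. Section 4 judges that estimate at p < 0.025 for each of the two co-primary outcomes.

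For the AIC step, the SAP does not say whether a parameter is one coefficient or a whole term. It gives no order or hierarchy of removal and names no protected terms.

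**The concern.** The two consecutive sentences describe different procedures. Optimising AIC means dropping whatever lowers it. The specific rule demands a fall of at least 2, which is the upper bound of what one parameter can deliver. Two analysts, each following one sentence, would reach different final models from the same data.

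The step decides which model yields both primary estimates. The SAP's opening paragraph also says it was finalised after preliminary descriptive analyses of partial data that included outcome rates over time. A selection rule that cannot be followed as written leaves the analyst to choose a workable reading at a point when some outcome data have been seen.

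**Working it through.** **Inputs, all from SAP section 3.2**
- Threshold: a reduction of at least 2. This is the only figure the SAP gives on the point, so there is no stated result to reproduce.
- Estimation during selection: maximum likelihood, so AIC = 2k − 2 ln L.
- Factors: "interaction between region (five regions) and the intervention-by-time spline term"; "interaction between facility level (three levels) and" the same term; and SBBC-I as yes/no. These carry 4, 2 and 1 df per spline column.
- Spline df: not given. The convergence steps allow it to fall to linear time, that is, one column.

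**Step 1: the identity.** Remove q parameters, keeping the data and random effects the same:

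reduction in AIC = [2k − 2 ln L(full)] − [2(k − q) − 2 ln L(reduced)] = 2q − LR,

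where LR = 2[ln L(full) − ln L(reduced)] ≥ 0. The reduction can never exceed 2q.

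**Step 2: one parameter.** With q = 1 the reduction is 2 − LR. Requiring at least 2 means LR ≤ 0, so LR = 0 and an estimate of exactly zero. The probability of this is essentially nil.

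**Step 3: numerical check.** In 1,000 simulated ordinary logistic data sets with no true effects (assumed: 4,000 records, 5% event rate, one continuous covariate, one five-level factor), the largest 1-df reduction was 1.999998 for the covariate and 1.9999996 for a single factor column. None reached 2, although about 85% of removals lowered AIC. Removing the 4-df factor as a block met the rule in 78.8% of data sets (theory: 80.1%).

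**Step 4: whole-term removal.** The stated rule becomes 2q − LR ≥ 2, that is LR ≤ 2q − 2. Plain AIC optimisation is LR < 2q. With the chi-square distribution on q df:

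| q | Stated rule: LR limit | p cut-off | Chance a null term is dropped | Plain AIC: LR limit | p cut-off | Chance a null term is dropped |
|---|---|---|---|---|---|---|
| 1 | 0 | 1.00 | 0 | 2 | 0.157 | 0.843 |
| 2 | 2 | 0.368 | 0.632 | 4 | 0.135 | 0.865 |
| 4 | 6 | 0.199 | 0.801 | 8 | 0.092 | 0.908 |
| 8 | 14 | 0.082 | 0.918 | 16 | 0.042 | 0.958 |

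**Step 5: which terms are affected.** With linear time, and all factor combinations present, the interactions with intervention-by-time have these df: region 4, facility level 2, SBBC-I 1, region × level 4 × 2 = 8, region × SBBC-I 4, level × SBBC-I 2, and all three 8. The SBBC-I interaction then has 1 df and cannot be removed even as a whole term. With a spline of s columns, each df is multiplied by s.

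**Step 6: the unit matters.** Take the 4-df region interaction with LR = 6. As a block, the reduction is 8 − 6 = 2 and the term goes. Coefficient by coefficient, each reduction is 2 − LR with LR > 0, so nothing goes. With LR = 7 the block reduction is 1: optimising AIC drops the term, and the stated rule keeps it.

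**The case against.** The strongest reply is that the model is built from whole terms, most with several df, and that the stated aim is clear. Read term by term, the rule works: a null 8-df term is dropped about 92% of the time. The convergence steps can also strip out interactions and spline df. This stands against the inference, which a reader might draw, that the model can never be simplified. That holds only for coefficient-wise removal within the AIC step. It does not rescue 1-df terms, and it does not tell the analyst which reading applies.

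Other stronger readings are also not supported:
- *A cut-off that changes with block size is itself an error.* Ordinary AIC does the same (0.157 to 0.042 from 1 to 8 df). The fault is the unstated unit and the unreachable 1-df threshold.
- *The variance of the relative risks will be inflated.* The SAP gives no event counts. The estimate is also averaged over cells by g-computation, so imprecise cell-level terms need not carry through in proportion.
- *The model has 90 or 120 intervention-by-time parameters.* Those counts are 5 × 3 × 2 = 30 cells times an assumed 3 or 4 spline df. They also need every cell to be populated, although only 30 facilities come from phase I. Linear time gives at most 30.
- *The intervention indicator could be selected out.* It has 1 df, so under the present wording it cannot be. Protection becomes necessary once the threshold is corrected.
- *REML is undefined here.* REML-type approximations exist for generalised linear mixed models, and section 8 allows R as well as Stata. The sentence is under-specified, not impossible.

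**Conclusion.** The point holds in limited form. As worded, the AIC rule removes no single parameter, while the sentence before it would remove one whenever LR < 2 (p > 0.157). Read term-wise, it removes multi-df terms under a stricter condition than AIC optimisation (LR ≤ 2q − 2 instead of LR < 2q) and still removes no 1-df term. The rule contradicts its stated aim, and the final model for both co-primary relative risks depends on an unstated unit of removal.

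The algebra is exact for nested maximum likelihood fits with the same data and random effects; only quadrature or convergence error could mimic an exact zero. The p cut-offs rest on the usual chi-square approximation. The size and direction of any change in the relative risks or their precision cannot be derived from the SAP.

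The REML sentence is a secondary matter. Standard REML belongs to linear mixed models, so its use for a logistic mixed model needs a named method.

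**What to change.** Replace the removal sentence in section 3.2 with: *Whole interaction terms (all df of a factor or spline together) are considered for removal, highest order first and respecting hierarchy, and a term is removed if its removal lowers the AIC; the intervention indicator, its main time spline and the adjustment covariates are always retained.*

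This follows the aim the SAP already states. A different rule, such as dropping a term unless AIC rises by at least 2, has a 1-df cut-off of 0.046 instead of 0.157. If that was intended, it should be written instead; the two should not stand as alternatives.

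In the estimation sentence of the same section, either keep maximum likelihood for the final logistic mixed model or name the REML-type approximation and the software that will provide it.

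The cost is two sentences, with no extra data and no added analysis. The change should be dated and made before the primary models are fitted.

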3.3 Statistical process control to study time to effect

Cumulative sum chart (CUSUM) procedures will be used to monitor for changes in each of the outcome variables throughout the intervention period. The CUSUMs will be based on logistic regression models estimated from the baseline data (Steiner et al, 2000). An overall CUSUM plot, risk-adjusted for region, facility level, and whether a facility was part of SBBC phase I or not will be

constructed. In addition, separate plots will be constructed per region, facility level, and SBBC-I (yes/no), as we anticipate substantial differences both in baseline levels and intervention effects between the levels of these factors. The signal limit for the CUSUM will be set according to a probability of 5% of getting a false alarm during 100 000 births in case there is no change from the baseline.

3.4 Exploration of contextual and implementation fidelity predictors of outcome trends during the intervention period

To explore facility-level factors predicting change in clinical outcomes during the intervention period, we will analyze monthly aggregated data from each facility using mixed effects Poisson regression. Random effects will be used to model dependency in data from the same facility. Development of outcome rates during the intervention period will be modelled non-linearly using splines and accounting for the number of births in each facility in each month. Candidate time-fixed predictor variables are region, facility level, average no. of births per month in the baseline period, baseline levels of outcomes, staff density, and readiness level. Effects of these will be assessed by interaction terms between the variable and the splines functions of intervention month. Effects of time-varying predictors like degree of uptake of new routines (use of Moyo and NeoBeat), and (cumulative) amount of training and mentorship involvement will be assessed by their rate ratios, assuming lagged (by one month) effects of training and mentorship involvement.

Adjustments will be made for monthly rates of referrals-in, births with not heard/detected FHR, and preterm births for each facility. Since these, as well as data regarding use of Moyo and NeoBeat, are only available for a substantial proportion of births from August 2024 and onwards, adjusted results and results for the latter predictor variables will be presented for the period August 2024 to December 2025. Unadjusted results, and results adjusted for BW, mother's age, and multiples, will be presented for the whole intervention period whenever possible.

In these analyses, the 30 SBBC-I facilities and the 122 new facilities will be analyzed separately.

4 Reporting and multiplicity considerations

Due to the non-randomized pre-post design of the study no causal claims will be made based on the estimated effects/associations.

All estimates will be presented with 95% confidence intervals (CI) and corresponding p-values from significance tests. For the estimates of overall efficacy for the two co-primary outcomes, p-values <0.025 will be considered statistically significant. All other p-values will be interpreted as exploratory.

If a confidence interval goes beyond the region of possible values for the parameter, we will report the interval truncated to possible values.

5 Graphical displays of results

Results from the main analyses will be supplemented with prediction plots based on the final models.

Furthermore, to accompany the CUSUM plots and illustrate the impact of the intervention over time, variable life adjusted displays (VLAD) will be made (Lovegrove, 1997). These plots will be made by aggregating the difference between the estimated conditional probability for fatal outcome based on a model estimated from baseline data, and the observed outcome, and can thus be interpreted in terms of estimated numbers of lives saved. The same logistic regression models as used for the CUSUM plots described in Section 3.3 will be used to estimate the probability of fatal outcome under baseline conditions.

For the promotor/inhibitor analyses, estimated marginal rates will be presented over time for each considered factor, based on the Poisson regression models.

6 Missing data and sensitivity analyses

The main efficacy analysis will be based on the available cases, assuming missing completely at random (MCAR) missingness in covariates (preliminary assessment of amount of missingness <1%) and missing at random (MAR) missingness in the outcome variables. We do expect some missingness in the outcome variables. For assessing sensitivity to different assumptions regarding missing data in the primary outcomes, perinatal death and 7-days maternal death, we provide sensitivity analyses based on missing not at random (MNAR) best/worst-case scenarios:

- As best-case scenarios we assume all missing being non-fatal outcomes.
- As worst-case scenario for perinatal death, we assume the following missing being fatal outcomes: referred-out cases; birth by CS; BW<1500 grams or missing; those requiring resuscitation using ventilation; low Apgar score (i.e., <7) at 5 minutes, or, if missing at 5 minutes, Apgar score <7 at 1 minute. The rest are assumed non-fatal cases.
- For maternal outcome we assume all missing with antepartum stillbirths, eclampsia, labour complications (3-degree tear, retained placenta, postpartum bleeding, blood transfusion), and referred-out cases to be fatal outcomes in the worst-case scenario.

7 Supplementary and supporting analyses

As a supplement to the main results in 3.2, marginal RRs will be presented according to combinations of factors (region, facility level, SBBC-I) and for different time points in the intervention period.

Although the intervention does not include means to reduce ASB, and does not target directly 2-7 days mortality, these outcomes are adjacent to the primary perinatal outcome and may be influenced indirectly, either due to changes in reporting or through possible postponement of the death event. Thus, it is of interest to assess potential changes in these indicators as well. For this, we will provide plots showing trends in rates of ASB and 2-7 days newborn deaths over the study period.

For the new SBBC-II sites, we have two sources of baseline data, each with its own limitations and merits. The retrospective data from 2023 and two first months of 2024 are not affected by the intervention in any way and represent a large sample. On the other hand, the data quality is expected to be lower than for the prospective data and with under-reporting of mortality. The prospective baseline data were collected in a period with preparation for the intervention, training of champions, probably increased awareness of optimal birth care, and possibly a Hawthorne effect related to the awareness of being observed/"measured". The data quality is more similar to that of the data collected during the intervention period, but the sample size is smaller than for the retrospective baseline data.

The relative effects of the expected more complete reporting of poor outcomes and the impact of the preparations in the prospective baseline data are unknown, but we believe that the underreporting in the retrospective data is substantial. We will present some analyses comparing the prospective and the retrospective baseline data, to inform the discussion of results of the main analyses.

8 Software

The analyses will be performed in Stata version 18 and R version 4.5.1, or newer versions.

9 References

ISRCTN92381311. Scaling up safer births bundle of care - keeping more mothers and babies safe during and after birth. ISRCTN Registry; 2025. Available at: https://www.isrctn.com/ISRCTN92381311.

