2.2 Covariates

In Table 1 an overview of covariates considered relevant for the clinical outcomes are listed. These variables are considered to be the most relevant prognostic factors, without too serious reliability and missingness issues.

Table 1: Overview of covariates relevant to include in the modelling

Covariate	Available period (baseline/intervention)	Available at level (individual/facility)	Fixed or time- varying	Details	Comment
Child	, ,	, , , , , ,	, 0		
Birth weight	Both	Individual	Time-varying	Grams	
Sex	Both	Individual	Time-varying	Male, female, ambiguous, or unknown	Ambiguous and unknown regarded as missing
Mother/pregnancy					
Age	Both	Individual	Time-varying	Years	
Parity	Both	Individual	Time-varying	Mother's number of previous births	
Multiples	Both	Individual	Time-varying	Number of fetuses	Dichotomize into one or more than one
ASB	Both	Individual	Time-varying		Adjustment variable for maternal outcome; ASB excluded for perinatal/newborn outcomes
Source of admission ¹	Intervention	Facility	Time-varying	Home, referral, or unknown → monthly proportions of referral-ins (unknown disregarded)	
Fetal heart rate (FHR) at admission ¹	Intervention	Facility	Time-varying	Heard/present, not heard/not present, or not measured/unknown → monthly proportions of not heard/present (not measured/unknown disregarded)	
Term/preterm ¹	Intervention	Facility	Time-varying	Term or preterm → monthly proportions of preterm	
Use of Moyo ¹	Intervention	Facility	Time-varying	Yes, no, or unknown → monthly proportion of births where Moyo used	
Facility					
Region	Both	Facility	Fixed	Five regions	

Level of health	Both	Facility	Fixed	Health center, district hospital,	
facility				or regional referral hospital	
Staff density	Both	Facility	Fixed	Number of healthcare workers at the	Assume representative
				facility at the start of the intervention	for the whole study
				period, divided by the average number	period
				of births per month at the facility	
				during the intervention period,	
				multiplied by 100	
Readiness level	Baseline	Facility	Fixed	0-100	
Training data – Team	Intervention	Facility	Time-varying	Monthly amount of team scenario	
training				training (average 5 persons involved)	
				divided by number of staff. Assume	
				effect lagged by one month. Also	
				consider cumulative amount of	
				training.	
Training data –	Intervention	Facility	Time-varying	Monthly amount of individual skill	
Individual skill				training divided by number of staff.	

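### The stated CUSUM and VLAD risk adjustment leaves out individual covariates that Section 3.2 uses, so a case-mix shift within strata could pass for improvement or harm

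*SAP*

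**What the plan says.** On the charts, SAP Section 3.3 states: "The CUSUMs will be based on logistic regression models estimated from the baseline data". The overall plot is "risk-adjusted for region, facility level, and whether a facility was part of SBBC phase I or not". Separate plots by region, by facility level and by SBBC-I status are also planned, with no adjustment set given for them. The signal limit is set so that a false alarm has 5% probability over 100,000 births if nothing has changed from baseline.

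On the VLAD, Section 5 says: "The same logistic regression models as used for the CUSUM plots described in Section 3.3 will be used" to give the probability of death under baseline conditions. The result "can thus be interpreted in terms of estimated numbers of lives saved".

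On the covariates, the row in Table 1 (Section 2.2) reads "Birth weight Both Individual Time-varying", and mother's age, multiples and ASB are listed the same way. Section 3.2 adjusts the main model for birth weight (with a category for missing values), mother's age (non-linear) and multiples, "which all were found to have some adjustment effect in SBBC-I", and for ASB with the maternal outcome. Section 3.4 also plans results adjusted for the first three. Section 6 puts covariate missingness below 1%.

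On case mix, Section 3.2 expects no change in the population over the study. It adds that the adjustments matter mostly for comparisons between regions, facility levels and SBBC-I status, "where changes in referral patterns among the participating facilities during the intervention may play a role".

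**The concern.** The three named factors are fixed attributes of a facility. Two births in the same combination of region, level and SBBC-I status therefore get the same expected risk, whatever the birth weight or number of fetuses. If the mix of births within such a cell changes after baseline, the observed deaths move and the expected deaths do not. The chart cannot tell that apart from an effect of the intervention.

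The separate plots are drawn by the very factors for which Section 3.2 names changed referral as a possibility. Section 3.3 gives no reason for leaving out covariates that are to hand and used elsewhere in the plan. At stake are the time-to-effect signals, the nominal 5% false-alarm probability and the count of lives saved.

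**Working it through.** **The plan's own figure.** The 5% false-alarm probability is a calibration target. Section 3.3 gives no signal limit, baseline death rate or odds ratio to which the chart is tuned, so the figure cannot be reproduced.

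**Single-covariate illustration.** Let s0 and s1 be the share of low-birth-weight births before and after a shift, and R the risk ratio of death for low against normal birth weight. With care unchanged, the true death rate changes by the factor

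(1 − s1 + R·s1) / (1 − s0 + R·s0).

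A model without birth weight keeps predicting the baseline rate, so this factor is the spurious relative risk. The values of s0, s1 and R are assumptions; the SAP gives none of them.

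- s0 = 0.10, s1 = 0.12, R = 6: (0.88 + 0.72) / (0.90 + 0.60) = 1.60 / 1.50 = 1.067, or 67 apparent excess deaths per 1,000 predicted.
- s0 = 0.10, s1 = 0.13, R = 6: (0.87 + 0.78) / 1.50 = 1.65 / 1.50 = 1.100, or 100 per 1,000 predicted.
- s1 = s0: the factor is 1 and there is no bias.

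**False-alarm probability and VLAD drift.** A log-likelihood-ratio CUSUM was simulated over 100,000 births, with its limit calibrated to 5% under no change (check runs gave 2.5–6.5%). The whole stream was then given a shifted low-birth-weight share, with no intervention effect. Assumed inputs: baseline death rate 0.5–2%, baseline share 10%, R = 4 to 8, chart tuned to an odds ratio of 0.75 for a decrease or 1.33 for an increase. Each shifted scenario had 500 runs, so the percentages are approximate.

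| Low-birth-weight share | Spurious RR | False alarms (target 5%) | VLAD drift per 100,000 births |
|---|---|---|---|
| 10% to 9% | 0.96–0.98 | 8–23% (improvement) | 12–82 lives saved |
| 10% to 8% | 0.92–0.95 | 16–61% (improvement) | 23–165 lives saved |
| 10% to 11% | 1.02–1.04 | 6–15% (harm) | 12–82 excess deaths |
| 10% to 12% | 1.05–1.08 | 15–50% (harm) | 23–165 excess deaths |

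The drift is births × baseline rate × (factor − 1). At R = 4 and a share of 12% the factor is 1.36 / 1.30 = 1.046, so 100,000 × 0.005 × 0.046 = 23. At R = 8 it is 1.84 / 1.70 = 1.082, so 100,000 × 0.02 × 0.082 ≈ 165.

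**With birth weight in the baseline model.** The average predicted risk moves by the same factor as the true risk. Drift from that covariate is then zero in expectation, provided the model is correctly specified. This follows from how the chart is built and was not simulated separately.

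These figures treat birth weight as a risk factor for perinatal death. Nothing was calculated for maternal death.

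**The case against.** The strongest reply is that the SAP expects no population change and says only that referral changes may play a role. Without a shift within strata there is no bias. That stands: the problem is conditional, and the sizes above rest on inputs from outside the SAP. A reader might infer that the charts will mislead; the documents support only that they could.

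A reader might also infer that the separate charts are planned without individual adjustment. The SAP does not say so; it states no set for them. One could even read the covariate paragraph of Section 3.2 as covering all analyses, but Section 3.3 names a specific set for the overall chart without those covariates, so the two passages need reconciling on any reading. Nor are the covariates complete for every birth: some missingness, below 1%, is expected.

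The fix is also only partial. Section 3.2 reports that fetal heart rate at admission was by far the most important individual adjustment variable for perinatal death in phase I, with referral-in of some importance. Neither these nor preterm status has baseline data here, so none can enter a baseline-fitted model, and a referral shift may act largely through them. Section 7 further believes that under-reporting in the retrospective baseline data is substantial; that distorts the baseline risk directly, and extra covariates do not correct it. Both points stand as limits on the fix. They give no reason to omit what is available.

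Finally, adjusted counterparts exist: Section 7 plans marginal relative risks by region, level, SBBC-I status and time point, and Section 3.4 has adjusted results. Section 4 treats p-values outside the co-primary estimates as exploratory and disclaims causal claims. This limits the consequences, but the CUSUM remains the plan's time-to-effect analysis and the VLAD its display of lives saved.

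**Conclusion.** The concern holds in conditional form. The stated adjustment set for the overall CUSUM, carried into the VLAD, omits individual covariates that the SAP has in both periods and uses in its main model, without a reason. If case mix shifts within strata, the charts could show spurious improvement or harm and the 5% limit would not be kept. The size cannot be determined from the SAP. Under the assumed inputs, a change of two percentage points in the low-birth-weight share gives a spurious relative change of roughly 5–8%.

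It would be wrong to conclude that the primary result is compromised. The relative risk at 1.5 years comes from the Section 3.2 model, which contains these covariates. Nor would disagreement between a chart and that relative risk by itself prove an error, since a cumulative chart and an effect at one time point measure different things. This is an inexpensive correction to secondary analyses.

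**What to change.** In Section 3.3, specify that the baseline logistic models for all CUSUM charts, overall and separate, include birth weight category (with its level for missing values), mother's age (non-linear) and multiples, plus ASB for maternal death. Region, facility level and SBBC-I status stay in the models, except where a chart holds one of them constant. Recalibrate the signal limits with these models. State in Section 5 that every VLAD uses them too.

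Add a sentence saying that confounding by fetal heart rate at admission, referral-in and preterm birth remains, because these variables have no baseline data, and that the lives-saved reading is subject to this.

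The cost is a few model terms and the recalibration. No new data are needed, and the primary analysis does not change.
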